Adverse pregnancy outcomes of interest in this study are spontaneous abortions, ectopic pregnancy, elective termination of pregnancy, stillbirth, infections requiring hospitalisation during pregnancy and emergency caesarean section. In addition, a composite outcome of foetal loss, defined as the presence of at least one of the following: spontaneous abortions, ectopic pregnancy, elective termination of pregnancy and stillbirth will be investigated.

Adverse birth outcomes

Adverse birth outcomes of interest in this study are preterm birth and SGA.

Exploratory outcomes

Select pregnancy loss outcomes (composite of spontaneous abortion and stillbirth) will be analysed by exposure period according to specific pregnancy trimesters (trimester 1 only; trimester 1&2 only; trimester 2&3 only; trimester 3 only; all trimesters 1&2&3) and MCM will be classified by body system organ class according to the EUROCAT categories Guide 1.5.

Adverse outcome related to growth up to one year of age will be a dichotomous variable defined as a composite outcome based on the presence of at least one of the following conditions: abnormal head circumference growth, stunting, or wasting. The period of assessment will be from birth until the end of the first year after birth.

Data sources

The study will make secondary use of existing data from five countries which have been selected based on a feasibility assessment conducted between July 2022-January 2023. The selected countries are:

- Denmark
- Finland
- France
- Germany
- USA

Study size

Sample size and power calculations were carried out separately for each of the primary outcomes of interest (MCM and select pregnancy loss outcomes) at the meta-analysis level. First, the **total number of SLE pregnancies** in the data sources were estimated using either the annual number of SLE pregnancies obtained in the feasibility assessment or the number of annual live births captured by the data sources (with assumptions on database coverage and proportion of live births/pregnancies in SLE patients) in cases where the data sources did not provide estimates in the feasibility assessment.

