Secondary objective 5c-d, 10 & 11	Describe and estimate risk of adverse pregnancy outcomes. Estimate relative risk of adverse pregnancy outcomes. Describe cohort demographic and clinical characteristics. Among live offspring	Unexposed study population	birth_unexp	INCLUSION: 
• Pregnancies with linkage mother-offspring within the study time period EXCLUSION: 
• Pregnancies exposed at any time to anifrolumab (+16 weeks prior to LMP2) (see Section 9.3.1)• Adopted children (where available)
Exploratory cohort infant (infant_exp+ infant_unexp)				
Secondary objective 5c-d; Exploratory 12	Describe and estimate the risk adverse outcomes related to infant growth. Describe cohort demographic and clinical characteristics. Among live offspring	Exposed study population	infant_expSLE	INCLUSION: 
• Live offspring• Pregnancies exposed at any time to anifrolumab (+16 weeks prior to LMP2)• Pregnancies with linkage mother-offspring within the study time period EXCLUSION: 
• Adopted children (where available)• Preterm offspring born <37 gestational weeks
Secondary objective 5c-d; Exploratory 12	Describe and estimate the risk adverse outcomes related to infant growth. Describe cohort demographic and clinical characteristics. Among live offspring	Unexposed study population	infant_unexpSLE	INCLUSION: 
• Live offspring• Pregnancies with linkage mother-offspring within the study time period EXCLUSION: 
• Pregnancies exposed at any time to anifrolumab (+16 weeks prior to LMP2) (see Section 9.3.1)• Adopted children (where available)• Preterm offspring born <37 gestational weeks

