For the adverse birth outcomes, the **index date**, included in the enrolment, will be defined as the delivery/birth date from which the offspring will be followed up for the outcome of interest. The **exit date/end of follow-up** will be defined as the end of the study period, death, emigration (where available), loss to follow-up (disenrollment/de-registering), or 1 day after delivery/birth, whichever is the soonest. The list of the adverse birth outcomes and their respective ICD-10 codes are presented in [Table 25](#).

- **Preterm birth:** defined as live births less than 37 weeks of gestation (<37 weeks)
- **SGA:** is defined as a birth weight lower than the 10th percentile of the distribution of birth weights among live births, by gestational age and sex, using a validated global reference for foetal weight and birthweight (76).

Exploratory outcomes

For the exploratory outcomes, the **index date/start of follow-up** and **exit date/end of follow-up** for MCM will be defined as in Section 9.3.2 MCM will be classified also by body system organ class according to the EUROCAT categories Guide 1.5 (section 3.3 in EUROCAT Subgroups of congenital anomalies) (41).

The full list of ICD-10 codes for MCM of interest can be found in Table 22.

Adverse outcomes related to infant growth up to 1 year of age

For the adverse outcomes related to infant growth, the **index date/start of follow-up**, included in the enrolment, will be defined as birth date from which the offspring will be followed up for the outcome of interest. The **exit date/end of follow-up** will be defined as the end of the study period, death, emigration (where available), loss to follow-up (disenrollment/de-registering), reaching the age of 1 year or date of first diagnosis of the outcome at study, whichever is the soonest.

Infant growth up to one year of age:

- Length (any time point during the first year of life – as available)
- Weight (any time point during the first year of life – as available)
- Head circumference (any time point during the first year of life – as available)

Adverse outcome related to growth up to one year of age will be a dichotomous variable defined as a composite outcome based on the presence of at least one of the following conditions: abnormal head circumference growth, stunting, or wasting. The period of assessment will be during the first year of life and the outcome will be assessed whenever anthropometric measurements are

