available. The offspring will be classified as subnormal growth if meeting at least one of the recommended WHO cut off values below at any time during the first year of life (119):

- <-2 SD z-score (equivalent to 2.3rd percentile) of head circumference-for-age based in the WHO 2006 growth charts.
- <-2 SD z-score (equivalent to 2.3rd percentile) of length-for-age to define stunting based in the WHO 2006 growth charts.
- <-2 SD z-score (equivalent to 2.3rd percentile) of weight-for-length to define wasting, based in the WHO 2006 growth charts (119).

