The Optum DAPI is sourced from a large proprietary administrative health care claims research database that covers members of a large national health insurer affiliated with Optum. The database contains medical and pharmacy claims, outpatient clinical laboratory results, socioeconomic measures, and patient enrolment data, dating back to 1994. The DAPI and Carelon Research databases draw from different insurance providers. Therefore, duplications could occur in instances where a patient is covered by both insurers (as primary or secondary), in which case the duplicate will be identified by hashing identifiers or linkage. However, duplication of data on events will not be expected as patients will be sourced from claims, which are derived from different insurance providers.

Within the Optum data source, these administrative claims data can be used to identify pregnancies and link the health care data of mothers with that of their infants. Data of mothers and infants is linked through a family identifier and by matching the dates of delivery and infant's birth. The fraction of identified deliveries that cannot be matched to an infant is likely due to the infant being carried under a different health insurance from the mother, in other instances, this is due to pregnancies that did not end in a delivery. Because the linkage is made within an identifiable health insurance database affiliated with Optum, Optum can (with appropriate approvals) access medical records for mothers or infants to ascertain covariate information and/or to confirm outcomes.

Study-specific data availability

The estimated annual number of pregnancies in women with SLE eligible for the MCM analysis and the select pregnancy loss outcomes analysis is 125 and 178, respectively (see Section 9.5.1 and Table 9).

Mother-offspring linkage is available since 1994 and 85% of live births can be linked. This linkage is achieved using a deterministic approach.

In the USA, anifrolumab received FDA approval in July 2021 and entered the market in August 2021.

In DAPI, information on drugs dispensed through retail pharmacies is available. In outpatient and inpatient settings, data on drugs taken by oral route may not be available, whereas data on drugs administered as a procedure would be available via procedure codes.

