USA (DAPI)	2007	4% ¹⁰	223	3-6	Available	Available	Available	Available	Available	Partial: - May be extracted from medical records for subset of patients	- Ability to capture anifrolumab exposure and primary outcomes - Number of pregnancies captured

Abbreviation used in the table: NA, Not available; CM, Congenital malformation; SOC, Standard of care; SLE, Systemic lupus erythematosus; UK, United Kingdom; USA, United States of America; MCM, Major congenital malformation; mCM, minor congenital malformation; ICD-10 GM, International Classification of Diseases 10th Revision German Modification; SGA, Small for gestational age; DCIR, Données de Consommation Inter-Régimes; PMSI, Programme de médicalisation des systèmes d'information

¹ Estimates for the annual number of pregnancies in women with SLE was directly provided by Carelon Research, DAPI and RHEKISS. For the other data sources, an estimate for the annual number of pregnancies in women with SLE was computed (see Section 9.5.1).

² Exposure to anifrolumab was based on the availability/information of biologics (in general) and belimumab (Benlysta) as a proxy for utilisation of anifrolumab.

³ Refers to major and minor congenital malformations.

⁴ Refers to ectopic pregnancy, spontaneous abortion, elective termination of pregnancy, stillbirth, infections requiring hospitalisation during pregnancy, and caesarean section.

⁵ Refers to preterm birth and small for gestational age.

⁶ Varies by the component registers.

⁷ Only high-cost hospital administered drugs are captured in SNDS. Therefore, exposure to anifrolumab can only be captured provided it is among the list of high-cost drugs.

⁸ RHEKISS is a nationwide, multi-centre registry for pregnancies in rheumatology and includes rheumatologist and patient reported data in the form of electronic case reports. As of July 2022, the registry includes 1907 patients (about 270 patients per year from 2015 onwards).

⁹ Approximately 20% of USA population (75 million) have ever been recorded by Carelon Research, and approximately 7% of USA population (21 million) are actively enrolled.

¹⁰ Approximately 21% of USA population (70 million) have ever been recorded by ORD, and approximately 4% of USA population (13 million) are actively enrolled.

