9.7.4 Exploratory objectives

The analysis for the exploratory study objectives will be conducted separately for each data source. The description of the analysis to be conducted for each exploratory study objective is provided in the following sections.

Objective 12

The analysis to describe and estimate the risk of adverse outcome related to infant growth up to one year of age in live offspring from the mothers who had moderate/severe SLE and were exposed or unexposed to anifrolumab during pregnancy (study objective 12) will be performed using the

infant cohort (as defined in Section 9.2.2). The crude and adjusted cumulative incidence (with corresponding 95% CI) of adverse outcome related to infant growth will be calculated for cases where mother was exposed to anifrolumab during pregnancy and for cases where mother was unexposed to anifrolumab during pregnancy. The crude cumulative incidence (i.e., risk) will be calculated as the total number of adverse outcomes related to infant growth divided by the total number of live offspring. The adjusted cumulative incidence (i.e., risk) will be estimated following PS adjustment.

Objective 13

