² There is no direct variable to determine hospitalisations due to infection. If an ICD-10 code for infection was used as the primary reason for health care visit, then it is captured in the national registers.

³ May be extracted from medical records for a subset of patients.

⁴ High completeness for weight and length/height (with dates) in the Children’s Database, but number and frequency of measurements are unknown.

⁵ Hospital visits with a linked ICD-10 code are available. Height and weight might be available from HILMO and AvoHILMO.

⁶ The database is used for planning and funding purposes and is subject to coding quality control.

Table 17: Availability of maternal characteristics, other baseline characteristics and covariates

Databases/Countries	USA		Denmark	Finland	France	Germany
	Carelon Research	DAPI	National Registers	National Registers	SNDS	RHEKISS
Date at first SLE diagnosis	Partial ¹	Yes	Yes	Yes	Yes	Yes (year)
Age at conception (LMP2)	No ²	Yes	Yes	Partial ³	Yes	Yes
Socioeconomic status at conception	No	Not provided	Yes	No	Yes (via proxy)	No
Ethnicity	No	Yes	No	No	No	No
Pre-pregnancy BMI	Partial ^{1,4}	Yes	Yes ⁵	Yes ⁵	No	Yes
Smoking (during pregnancy)	Yes	Yes	Yes	Yes	No	Yes
Alcohol and Substance abuse (during pregnancy)	Yes	Yes	Yes	Yes	No	Yes
Pre-pregnancy diabetes	Yes	Yes	Yes	Yes	Yes	Yes
Gestational diabetes	Yes	Yes	Yes	Yes	Yes	Yes
Pre-eclampsia	Partial ¹	Not provided	Yes	Partial ⁶	Yes	Yes
Previous spontaneous abortions	Partial ¹	Not provided	Partial ⁷	Partial ⁸	Partial ⁹	Yes
Previous stillbirths	Partial	Not provided	Yes	Yes ⁸	Yes	Yes
Previous elective terminations of pregnancies	Partial ¹	Not provided	Yes	Yes	Partial ⁹	Yes
Previous preterm births	Partial ¹	Not provided	Yes	Yes	Yes	Yes
Previous small for gestational age births	Partial ¹	Not provided	Yes	Yes	Yes	Yes
Laboratory results and date of testing ¹⁰	Partial	Not provided	Yes	Yes	No	Yes
Number of healthcare visits six months before LMP2 and during pregnancy ¹¹	Yes	Yes	Yes	Yes ¹²	Yes	Partial ¹³

Abbreviations used in the table: LMP2, Last menstrual period plus 2 weeks; SLE, Systemic lupus erythematosus; UK, United Kingdom; USA, United States of America

¹ These data are available through medical claims but may be incomplete if diagnosis occurred prior to entry into an Anthem health plan.

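### Exploratory Objective 12 counts infants with no growth measurement as non-cases, so the reported growth risk is too low wherever measurement is incomplete

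*Protocol*

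**What the plan says.** The outcome is a yes/no composite of three conditions: abnormal head circumference growth, stunting and wasting. Each is a z-score below -2 SD on the WHO charts (section 9.3.2). The case rule reads "The offspring will be classified as subnormal growth if meeting at least one of the recommended WHO cut off values below at any time" in the first year, using whatever measurements a source happens to hold. The Abstract sets the window: "The period of assessment will be from birth until the end of the first year after birth".

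For Objective 12, section 9.7.4 says the crude cumulative incidence is "calculated as the total number of adverse outcomes related to infant growth divided by the total number of live offspring".

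Table 5 (section 9.2.2) builds the infant cohort from live, linked offspring. It excludes adopted children and "Preterm offspring born <37 gestational weeks". No criterion asks for a growth measurement.

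The protocol knows that measurement is incomplete. For DAPI, Table 8 says of infant growth: "May be extracted from medical records for subset of patients". The footnote to Table 16 in Appendix C says the same: "May be extracted from medical records for a subset of patients". For Finland, height and weight are described only as possibly available. For Denmark, the number and frequency of measurements are unknown. Section 9.9 names first-year growth among the variables that some databases may lack.

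**The concern.** Numerator and denominator do not cover the same infants. Being a case requires a recorded length, weight-for-length or head circumference. Being in the denominator requires only live, linked, term birth. Linkage does not close the gap: in DAPI "85% of live births can be linked", but a linked infant may still have no growth record.

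Objective 12 has a single product, the absolute risk of adverse growth in each exposure group. If unmeasured infants count as healthy, that number is pulled down by an amount that depends on record-keeping rather than on growth. It will also differ between data sources for the same reason.

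**Working it through.** **The plan's own figure.** Section 9.3.2 equates -2 SD with the 2.3rd percentile. Φ(-2) = 0.0228, so this reproduces. The protocol gives no expected risk and no expected share measured for this outcome.

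**Effect of the denominator.** Let N be the live offspring in the cohort, m the share with at least one usable measurement, and p the risk among those measured.

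- Cases = N × m × p.
- Reported risk = N × m × p / N = m × p.
- Understatement relative to measured infants = p / (m × p) = 1/m.

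| m (assumed) | 1/m | Reported risk if p = 10% |
|---|---|---|
| 25% | 4 | 2.5% |
| 50% | 2 | 5% |
| 75% | 1.33 | 7.5% |

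If q is the risk among unmeasured infants, the risk in all live offspring is m × p + (1 - m) × q. The stated formula sets q = 0. It therefore gives the lowest value compatible with the data, and is right only if no unmeasured infant has subnormal growth.

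**Scale in DAPI.** Inputs: 162 exposed pregnancies (Table 11, 10% uptake, 2032 report); 80% ending in live birth (section 9.5.1.2); 85% of live births linked (section 9.4.1.5).

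- 162 × 0.80 × 0.85 = 110 over the full study period.
- The footnotes to Table 4 shorten the growth cohort: enrolment starts 9 months after launch, and the last infant must enter a year before the study ends. The footnote date is 29 September 2027. I assume 29 September 2029 for the USA, whose study period ends two years later.
- That leaves about 7.35 of 9.10 years. With even accrual, 110 × 7.35 / 9.10 = 89 exposed live births, before preterm births are removed.
- If m = 50% and p = 10%: 89 × 0.5 = 44.5 infants can be cases, 44.5 × 0.10 = 4.45 cases are expected, and the reported risk is 4.45 / 89 = 5%.

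**Between groups.** If m is equal in both groups, the ratio of reported risks is (m × p1) / (m × p0) = p1 / p0, which is undistorted. The difference shrinks to m × (p1 - p0).

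**The case against.** The strongest reply is that section 9.7 already covers missing data. It says missingness will be reported, names complete case analysis as a candidate, and leaves the methods to the SAP. Complete case analysis would give the measured-infant denominator. Section 9.7.1 also tabulates patients at risk and events, section 9.9 admits that growth data may be lacking, and the comparator comes from the same source under the same rule. The objective is exploratory and descriptive.

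Part of this stands. It limits the importance of the point, and the SAP could repair it. But section 9.7 only says that such methods will be considered, while section 9.7.4 states the formula. A SAP that follows section 9.7.4 reproduces the error.

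A reader might infer more than the protocol supports:

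- **A false difference between groups.** Measured shares of 70% and 50% would produce a ratio of 1.4 from nothing (0.7 / 0.5). Nothing in the protocol indicates that exposed and comparator infants are measured differently.
- **That counting birth values is an error.** For an in utero exposure it is defensible. Preterm infants are excluded, SGA is a separate outcome, and birth weight is described by group. Follow-up ends at "reaching the age of 1 year or date of first diagnosis of the outcome at study, whichever is the soonest", but stopping at the first event cannot change a yes/no cumulative incidence.
- **That the any-time rule is an error.** Any ever-in-the-first-year risk rises with the number of measurements. In simulated healthy infants, about 6% are flagged with one occasion, 8-11% with two and 11-18% with four. This assumes standard normal z-scores, correlations of 0.2-0.4 between indices and 0.6-0.9 between occasions. It is a reason to show measurements per infant as context, not to replace the rule.

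**Conclusion.** The point holds as a minor one. Taken as written, the Objective 12 formula treats unmeasured infants as non-cases, and the protocol itself expects such infants, most clearly in DAPI. The reported risk is the risk among measured infants multiplied by the share measured: half of it at 50% measured.

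The direction follows from the formula. The size rests entirely on the share measured, which the protocol does not give, so the factors 4, 2 and 1.33 are illustrations. The DAPI count of about 89 further assumes 10% uptake, even accrual and the shifted USA end date.

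No risk ratio or meta-analysis is planned for this outcome, and no primary or secondary conclusion changes.

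**What to change.** In section 9.7.4, Objective 12, make the denominator live offspring with at least one usable length, weight-for-length or head circumference measurement in the first year. Report the number and share measured by exposure group and data source, with the number of measurements per infant as context. The case rule can stay as it is.

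The cost is wording and a few table rows. There are three drawbacks. The denominator gets smaller. The measured infants may be a selected group, so their risk need not apply to all live offspring; showing the share measured lets the reader judge this. Small-number masking also applies: section 9.7 gives limits of 5 (Denmark, Finland), 10 (Carelon Research) and 11 (France), and some cells will be suppressed.

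Showing cases met only at birth separately, or adding a version at a fixed age, is an optional presentation choice and not a correction. In the exposed groups such splits would mostly fall below the masking limits.

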9.3.3 Participant's characteristics and potential confounders/risk factors

A broad range of characteristics and risk factors, related to mother and offspring, will be considered. These include, but are not limited to, demographic and clinical characteristics and concomitant comorbidities and medications (Objective 5). The final choice of characteristics, risk factors and confounders will depend on the availability of data and clinical relevance.

- **Demographic characteristics of the live offspring (at birth):** gender, gestational age, birth weight, Apgar score.
- **Demographic characteristics of mothers with SLE (before or at start of exposure):** maternal age, maternal socioeconomic status, and maternal ethnicity.
- **Maternal lifestyle characteristics (before or at LMP2):** smoking prior pregnancy, alcohol abuse prior pregnancy, substance abuse prior pregnancy, maternal weight and height or BMI (kg/m²) prior to pregnancy.
- **Maternal clinical characteristics:** SLE-related comorbid conditions, SLE SOC, SLE activity algorithm, co-medications (non-SLE SOC), selected autoimmune conditions (**before or at start of exposure**). Pre-pregnancy diabetes, pre-pregnancy hypertension (**before or at LMP2**).
- **Health Care Utilisation (HCU) (before or at LMP2)** in the 12 months prior to LMP2 will be use as proxy of burden of maternal comorbidities: number prenatal visits, number of outpatients and primary care visits, use of emergency department, hospitalisations (number of days, number of hospitalisations), type of health care providers visited.
- **Obstetric history (before or at LMP2):** gestational diabetes, pre-pregnancy pre-eclampsia, previous spontaneous abortion, previous stillbirth, previous preterm birth, and previous SGA birth.

The list of potential risk factors and confounders for the analysis of *MCM* and *mCM*, *adverse pregnancy outcomes* and *adverse birth outcomes* are summarised below in [Table 7](#), with further details in [Table 21](#). Factors listed as exclusion criteria for the selection of study population are

omitted from the potential risk factors ([Table 5](#)). The list of the ICD-10 codes for substance abuse, alcohol abuse, and diabetes, are presented in [Table 28](#), [Table 29](#), [Table 30](#), respectively.

Table 7: Potential confounders/risk factors of risk of MCM and mCM, adverse pregnancy outcomes and adverse birth outcomes in the offspring exposed *in utero* to anifrolumab vs unexposed *in utero* to anifrolumab

	CM	Adverse pregnancy outcomes						Adverse birth outcomes	
	MCM/mCM	Ectopic pregnancy	Spontaneous abortion	Elective termination of pregnancy	Stillbirth	Infections requiring hospitalisation during pregnancy	Emergency C-section	Preterm birth	SGA
Mother									
Age at conception (LMP2)	×	×	×	×	×	×	×	×	×
Socioeconomic status (before or at start of exposure)	×	×	×	×	×	×	×	×	×
Health care utilisation (before or at LMP2)	×	×	×	×	×	×	×	×	×
SLE-related comorbid conditions (before or at start of exposure)	×	×	×	×	×	×	×	×	×
SLE SOC (before or at start of exposure)	×	×	×	×	×	×	×	×	×
SLE activity algorithm (before or at start of exposure)	×	×	×	×	×	×	×	×	×
Autoimmune conditions (before or at start of exposure)	×		×	×	×		×	×	×
Co-medications (non-SLE SOC) (before or at start of exposure)	×	×	×	×	×	×	×	×	×
Smoking (before or at LMP2)	×	×	×	×	×	×	×	×	×
Alcohol abuse (before or at LMP2)	×	×	×	×	×	×	×	×	×
Substance abuse (before or at LMP2)	×	×	×	×	×	×	×	×	×
Gestational diabetes (before or at LMP2)								×	×
Pre-pregnancy obesity (before or at LMP2)	×		×		×		×	×	×
History of pre-eclampsia (before or at LMP2)	×				×				
Pre-pregnancy hypertension (before or at LMP2)	×				×	×	×	×	×

	CM	Adverse pregnancy outcomes						Adverse birth outcomes	
	MCM/mCM	Ectopic pregnancy	Spontaneous abortion	Elective termination of pregnancy	Stillbirth	Infections requiring hospitalisation during pregnancy	Emergency C-section	Preterm birth	SGA
Mother									
Pre-pregnancy diabetes (before or at LMP2)	×		×		×	×	×	×	×
Previous spontaneous abortions (before or at LMP2)	×		×	×	×			×	
Previous stillbirth (before or at LMP2)	×				×				
Previous preterm birth (before or at LMP2)								×	
Previous SGA (before or at LMP2)									×
Offspring									
Year of conception	×	×	×	×	×	×	×	×	×

- Omitted from this list are potential risk factors and/or potential mediators between SLE treatments and CM that are exclusion criteria in this study (as defined in Section 9.2.2):
 - *mother*: history of CM or chromosomal abnormalities and genetic syndromes before delivery and women prescribed a confirmed teratogenic drug (including but not limited to warfarin, angiotensin converting enzyme inhibitors, antineoplastic agents, isotretinoin, misoprostol, or thalidomide), at LMP2 with a look back period of 5-half-lives of relevant drug, to account for prescriptions/dispensations/administrations that may have led to exposure during pregnancy.
 - *offspring*: adopted children.

SLE Severity and Activity Identification

As anifrolumab is currently indicated for moderate and severe SLE, to select a comparable population, only pregnant women with moderate to severe SLE will be included in the main analysis.

Disease severity and activity are not directly obtained from secondary data sources, since validated indices that assess disease severity and activity are not systematically used in routine practice and therefore not recorded in most data sources. In this study, algorithms developed for use in secondary data base studies will be used (50, 66). The algorithm was derived in a USA claims data source (OPTUM) based on literature and clinical consultation. It combines elements of cumulative damage (exemplar code list provided in Table 26) and/or usage of SLE medications (exemplar code list provided in Table 19) based on the Systemic Lupus Erythematosus Disease Index (SLEDAI), Systemic Lupus Activity Measure (SLAM), British Isles Lupus Assessment Group Index (BILAG) indices, and a consensus of expert clinical opinion. The algorithm has been previously used in other settings and validated in the OPTUM research database (106). The validation was performed by comparing the Garris (50) SLE severity algorithm to the highest SLE Disease Activity Index-2000 (SLEDAI-2K) score in 100 patients with SLE treated at Brigham and Women's Hospital Lupus Center (2008–2010), over a 1-year period for each person, using SLEDAI-2K categories of mild (<3), moderate (3-6), and severe (>6). For classifying moderate/severe disease vs. mild, the algorithm has a sensitivity of 85.7%, specificity of 67.6%, positive predictive value (PPV) of 81.8%, and negative predictive value (NPV) of 73.5% (106). In this study, adaptations, based on expert rheumatologist advice, have been made to the Garris et. al. disease severity algorithm (50, 66, 106). These adaptations are the inclusion of the additional criteria based on IV, intramuscular, intra-articular, and soft tissue glucocorticoid injection, and the prescription of the biologics anifrolumab or belimumab, IV immunoglobulin G or plasmapheresis. For the SLE disease activity algorithm, IV and intramuscular corticosteroid were added to the severe and moderate disease activity. The prednisolone-equivalent dose was modified from 60 mg/day (severity algorithm) and 40 mg/day (activity algorithm) to 20 mg/day for both algorithms (Figure 7 and Figure 8).

The highest SLE severity classification experienced by a patient in the baseline period (maximum look-back period of 12 months prior to LMP2) and highest activity (maximum look-back period of 6 months prior to LMP2 and at the end of each trimester for the adverse birth outcomes) will be assessed using the severity and activity algorithms (Figure 7 and Figure 8). The severity algorithm will be used in the selection of the study population (see Figure 5) and each single component of the severity and activity algorithms will be considered for confounding adjustment.

[figure not shown]

Figure 7: SLE disease severity algorithm¹⁶

- SLE-related moderate manifestations: acute pancreatitis, chorioretinitis, demyelinating syndrome/acute inflammatory demyelinating polyradiculoneuropathy, episcleritis/scleritis, hemolytic anaemia, hepatitis (non-viral), ischaemic necrosis of bone, nephritis, renal impairment other than nephritis or end-stage renal disease, lupus enteritis/colitis, mononeuropathy/polyneuropathy, myelopathy, myocarditis, pericarditis, pleurisy/pleural effusion, pseudotumor cerebri, seizure, uveitis vasculitis (excluding aortitis)
- If a severe condition exists, the patient(s) will be moved to the severe category
- Rituximab (including reference product and biosimilars)
- SLE-related severe manifestations: acute confusional state/psychosis, aortitis, arterial/venous thrombosis, aseptic meningitis, cardiac tamponade, cranial neuropathy, intestinal pseudo-obstruction, end-stage renal disease, optic neuritis, pulmonary haemorrhage, stroke/transient ischaemic attack (TIA)

¹⁶ SLE-related manifestations further details are provided in Table 26. Abbreviations: IV, Intravenous; SLE, Systemic lupus erythematosus.

Periods of increased disease activity (flares, [Figure 8](#)) are categorised as mild, moderate and severe ([66](#)), if meeting one or all of the following criteria ([Figure 8](#)), and will be assessed as the highest disease activity experienced by a patient in the baseline period (maximum look-back period of 6 months prior to LMP2). Periods of increased SLE disease activity will also be assessed at the end of each trimester for the adverse birth outcomes. Other markers of disease activity will be retrieved whenever available: results of complements (C3, C4) ([5](#), [43](#)) or anti-double stranded DNA (anti-dsDNA) ([43](#)).

[figure not shown]

Figure 8: SLE disease activity algorithm¹⁷

- a. SLE-related moderate manifestations: acute pancreatitis, chorioretinitis, demyelinating syndrome/acute inflammatory demyelinating polyradiculoneuropathy, episcleritis/scleritis, hemolytic anaemia, hepatitis (non-viral), ischaemic necrosis of bone, nephritis, renal impairment other than nephritis or end-stage renal disease, lupus enteritis/colitis, mononeuropathy/polyneuropathy, myelopathy, myocarditis, pericarditis, pleurisy/pleural effusion, pseudotumor cerebri, seizure, uveitis vasculitis (excluding aortitis)

¹⁷ SLE-related manifestations further details are provided in [Table 26](#). Abbreviations: IV, Intravenous; NSAIDs, Non-steroidal anti-inflammatory drugs; SLE, Systemic lupus erythematosus.

- b. SLE-related severe manifestations: acute confusional state/psychosis, aortitis, arterial/venous thrombosis, aseptic meningitis, cardiac tamponade, cranial neuropathy, intestinal pseudo-obstruction, end-stage renal disease, optic neuritis, pulmonary haemorrhage, stroke/TIA

Additional considerations

Exposure to co-medications. *In utero* exposure (16 weeks prior to LMP2 to account for prescriptions/dispensations/administrations that may have led to exposure during pregnancy) to co-medications (122) (provided in [Appendix D. Exemplar Codelists](#)) will be assessed and considered for confounding adjustment.

Exposure to co-medications will be ascertained from recordings of outpatient visits, procedures, prescriptions, prescriptions dispensed at community pharmacies and insurance claims registrations as available in the different data sources. Co-medication will be identified using ATC codes (provided in [Table 27](#)). The list of co-medication of SLE-related comorbidities was based on literature (43, 55) and complemented by clinical experts' recommendations. The availability of information on exposure was explored as part of the feasibility assessment.

Exposure to co-medications in the 16 weeks prior to LMP2 will be investigated and considered as a risk factor for the primary and secondary outcomes. A polypharmacy index will be created. There is no consensus definition of polypharmacy (72). In this study, polypharmacy will be considered as a continuous variable, reflecting the cumulative number of the prescribed medications from other therapeutic classes (other than those specified for the treatment of SLE described in Section 9.3.1), within an interval of interest. This polypharmacy index will be considered for confounding adjustment. The rationale for considering polypharmacy as a potential risk factor is based on some evidence that polypharmacy may be associated with adverse events during pregnancy. Factors which may contribute to the foetal risk in polypharmacy include the pathophysiology of the underlying co-morbid conditions, adverse drug effects and the potential for drug-to-drug interaction (72, 111). In addition, polypharmacy may be an indication of severity of disease, with SLE manifestations in multiple organ systems requiring treatment (102).

Maternal age at conception. Maternal age at conception is considered a major risk factor for the studied outcomes. Multiple epidemiological studies have found a relation between advanced maternal age at conception and congenital malformations (57), adverse pregnancy (46), birth and infant outcomes (52). Although maternal age is not directly associated to the exposure of interest, it is associated with the severity of the disease and with the selected outcomes, thus this variable will be considered for confounding adjustment.

Gestational age. Is measured from the first day of the LMP and expressed in weeks and days, completed weeks, or in days. Gestational age is usually calculated from the reported LMP (depends on recall of the LMP and assumes that ovulations occurred on average 2 weeks after LMP). If gestational age is calculated from LMP, 2 weeks will be added to the time interval to estimate the conception date (LMP2). For data sources in which the LMP is missing, date of conception (equivalent to LMP2) will be estimated based on date of birth and gestational age at birth. In

countries where gestational age is calculated from conception, gestational age (in days) will be subtracted from the date of birth to obtain the date of conception.

Foetal biometric measures from ultrasounds are increasingly being used to confirm or adjust LMP. Current recommendations from the American College of Obstetricians and Gynaecologist, the Society for Maternal-Foetal Medicine, Euro-Peristat Network recommend use of the best obstetric estimate rather than LMP alone. Hence, in Europe, and USA, estimate of gestational age is based on ultrasound dating, and rarely based on LMP alone due to reporting errors (23). Thus, gestational age will be assessed using the best obstetric estimate available. Gestational age is rarely available for ectopic pregnancies or miscarriages.

